14.3.3. Secondary Efficacy Analyses

All secondary endpoints including change from Baseline in ABC-C_{FXS} Social Avoidance, Irritability, Inappropriate Speech, Stereotypy and Hyperactivity subscales scores and changes from Baseline in the ADAMS total score and subscale scores, will also be analyzed using the same MMRM approach as the primary endpoint.

The statistical comparison of active versus placebo for the CGI-I at weeks 4 and 8 will be based on Wilcoxon rank sum test. The statistical comparison of active versus placebo for the CGI-S will be based on a covariate adjusted Cochran-Mantel-Haenszel (CMH) test, adjusting for the baseline score as the covariate.

A patient will be considered as “improved” on the CGI-I scale if they are rated as “1-very much improved” or “2-much improved”. All other ratings, including missing values, will be considered “not improved” (Guy 1976; Berry-Kravis et al. 2017). The response rates for the percent of patients improved using CGI-I, and for patients having both $\geq 25\%$ improvement from Baseline in ABC-C_{FXS} Social Avoidance subscale score AND improved on CGI-I scale will be compared using the chi-square test and binomial confidence intervals.

Change from Baseline in Family Impact PedsQLTM will be analyzed using ANCOVA. ANCOVA models will contain fixed effects for treatment, region and study site with Baseline value for the dependent variable of interest as a covariate.

For MMRM/ANCOVA, descriptive statistics will be presented by visit, which will include LS mean, LS standard errors, LS mean treatment difference (active-placebo) and associated 95% confidence interval (CI) and p-values for between treatment group tests.

14.3.4. Exploratory Analysis

Results of exploratory analysis of the Caregiver Global Impression of Severity, the Caregiver Global Impression of Change, and the Qualitative Caregiver reported Behavioral Survey will be reported using descriptive statistics.

14.4. Safety Analysis

AEs will be tabulated by the actual treatment dose of trial drug received at the time of initiation of the adverse event and classified by system organ class and preferred term using MedDRA. Additionally, AEs will be tabulated overall (total number of AEs and total number of patients with AEs).

MADDERS[®] will be used in this study to systematically capture and adjudicate abuse-related events. (Treister et al. 2016). Data from the MADDERS[®] will be summarize and presented separately from other AEs.

Symptoms of withdrawal will also be assessed by comparing change over time in the total score on the MWC and total score on the PWC-20 from Baseline to Week 12/ET, weekly during the taper period and weekly for four weeks after the patient stops study drug.

Vital signs assessments (actual and change from Baseline) will be summarized using descriptive statistics and presented by actual treatment group.

Safety laboratory and urinalysis assessments (actual and change from Baseline) will be summarized by actual treatment group.

ECGs (actual and change from Baseline) will be summarized by actual treatment group. ECG results including any clinically significant findings will be summarized at each study visit.

Application site irritation check will be summarized using counts and percentages at each respective site check score ('0', '1', '2', '3', or '4') by actual treatment group.

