IEC	Independent Ethics Committee
IP	Investigational Product
IQ	Intelligence Quotient
IRB	Institutional Review Board
IRT	Interactive Response System
IV	Intravenous
kg	Kilogram
KO	Knock-out
LDL	Low density lipoprotein
L	Liter
LS	Least-squares
LTD	Long-term depression

Table 2: Abbreviations and Specialist Terms (Continued)

Abbreviation or Specialist Term	Explanation
MADDERS®	The Misuse Abuse and Diversion Drug Event Reporting System
MedDRA	Medical Dictionary for Regulatory Activities
mg	Milligram
mL	Milliliter
MWC	Marijuana Withdrawal Checklist
MMRM	Mixed effects models for repeated measures
MRI	Magnetic resonance imaging
MS/MS	Tandem mass spectrometry
N	Number
ng	Nanogram
nm	Nanometers
NOAEL	No-observed-adverse-effect-levels
NONMEM	Nonlinear mixed effects model
OA	Osteoarthritis
OAE	Other significant adverse event
OLE	Open Label Extension
OR	Odds Ratio
OTC	Over-the-counter
PASS	Power Analysis and Sample Size
PedsQL™	Pediatric Quality of Life Inventory
PI	Principal Investigator The investigator who leads the study conduct at an individual study center. Every study center has a principal investigator.
PK	Pharmacokinetic
PND	Post-natal day
PWC-20	Penn Physician Withdrawal Checklist
Q12H	Every 12 hours

Table 2: Abbreviations and Specialist Terms (Continued)

Abbreviation or Specialist Term	Explanation
RBC	Red blood cell
RNA	Ribonucleic acid
SAE	Serious adverse event
SAP	Statistical Analysis Plan
SC	Subcutaneous
SGOT	Serum glutamic oxaloacetic transaminase
SGPT	Serum glutamic pyruvic transaminase
SSRIs	Selective serotonin reuptake inhibitors
T	Testosterone
t _{1/2}	Half-life
TdP	Torsades de pointes
TEAE	Treatment emergent adverse event
THC	Δ ⁹ -tetrahydrocannabinol
UDS	Urine Drug Screen
ULN	Upper limit of normal
UK	United Kingdom
UV	Ultraviolet
VABS-3	Vineland Adaptive Behavior Scales™, Third Edition
VAS	Visual Analog Scale
VR1	Vanilloid type-1
vs	Versus
WBC	White blood cell
WDS	Withdrawal Discomfort Score

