7.4. Dose Schedule

Following the Screening period, eligible patients will start a single-blind Placebo Lead-In period for [REDACTED]. The placebo will be applied Q12H (± 2 hours). For patients ≤ 35 kg, each application will consist of one sachet of placebo containing 2.98 g of gel (two sachets in total per day). For patients > 35 kg, each application will consist of two sachets of placebo containing 2.98 g of gel in each sachet (four sachets in total per day).

At Visit 3, patients will be randomized to receive either ZYN002 or placebo. In a blinded fashion, ZYN002 treated patients who weigh ≤ 35 kg will receive 125 mg CBD Q12H (± 2 hours); total daily dose of 250 mg CBD. Patients who weigh > 35 kg will receive 250 mg CBD Q12H (± 2 hours); total daily dose of 500 mg CBD. All patients will remain on their assigned dose during the 12 weeks of the treatment phase of the study. Study visits will occur at Week 4 (Visit 4), Week 8 (Visit 5), and Week 12 (Visit 6). Patients who have successfully completed the 12 weeks of the double-blind study will have the option to enroll in an OLE study. Patients not taking AEDs and not continuing in the OLE study will complete their EOS procedures at Visit 6/ET. Patients on AEDs who are not continuing in the OLE study will taper off trial drug and then have their EOS Visit. Telephone Follow-Up calls will occur during the taper period and weekly for all patients who do not enter the OLE study for four weeks post the last dose of trial drug. At Visit 2, parents/caregivers will be instructed on proper application of the study gel (active/placebo gel). [REDACTED]

[REDACTED] Parents/caregivers will apply all trial drug to clean, dry, intact skin, thoroughly massaging it into the right and/or left upper arms and shoulders until the area is dry. The study gel will be rubbed in completely and must be dry prior to dressing.

[REDACTED] The application site should be covered to minimize sun exposure when going outside during the day. Parents/caregivers will

use gloves supplied by the Sponsor to apply the study gel. If redness occurs at the application site, the parent (after consultation with the Investigator) may switch the application site temporarily to the upper thighs.

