- d. For Patients taking concomitant AEDs and not continuing in the OLE or are discontinuing prematurely: At Visit 6/ET, patients \leq 35 kg will be reduced, in a blinded manner, total daily dose of 125 mg, over one week. For patients $>$ 35 kg, receiving 500 mg daily dose, the dose of trial drug will be reduced in a blinded manner over two weeks. During the first week of taper, the dose will be reduced to 125 mg Q12H; (ZYN002 or placebo) (\pm 2 hours); total daily dose of 250 mg, followed by a second week of taper from 250 mg total daily dose to total daily dose of 125 mg. After the one- or two-week taper, patients will discontinue from the study and attend EOS Visit.
- e. The Weekly Telephone Follow-Up calls will occur during the taper and weekly for four weeks post patient's last dose of trial drug for those patients not continuing on to the open-label extension study.
- f. Complete physical and neurological exam including height and weight at screening. Targeted physical and neurological exam at Visit 6/ET.
- g. Tanner Stage assessment performed on adolescent patients 10 to less than 18 years of age or earlier if clinically indicated by onset of menarche or other signs of precocious puberty.
- h. Vital signs include blood pressure, heart rate, respiratory rate, oral, infrared red forehead or tympanic temperature and will be recorded after the patient has been sitting for at least 5 minutes. Vital signs will be taken prior to blood draws. No food or drink is allowed 30 minutes before vital sign assessment.
- i. The ECG scheduled for collection at Screening may be completed at the Screening Visit or Visit 2.
- j. A serum pregnancy test will be completed at screening for females of childbearing potential. A serum or urine pregnancy test will be completed at Visits 4, 5, and 6 for females of childbearing potential.
- k. At Visit 2, all patients will receive placebo for [REDACTED]. At Visit 3, patients will be randomized to receive placebo or ZYN002. No trial drug will be administered on the patient's last day of study. If the patient is continuing into the OLE study, they will receive the first dose of OLE trial drug on the last day of the ZYN2-CL-016 study. On days of study visits, the trial drug will be applied at the study site during the visit.

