12.2.1. Definition of Adverse Events

12.2.1.1. Adverse Event (AE)

An AE is an undesirable medical occurrence (sign, symptom, or diagnosis) or worsening of a pre-existing medical condition (e.g., diabetes, congestive heart failure, rheumatoid arthritis, psoriasis) that occurs at any time after signing of the ICF whether or not it is considered to be related to treatment. Worsening of an existing medical condition is when a condition present at the time of signing of the ICF (e.g., cancer, diabetes, gout) becomes more severe, more frequent, or increased in duration during the study. Hospitalizations for pretreatment conditions (e.g., elective cosmetic procedures) or surgeries that were planned before entry into the study are not considered AEs. AEs will be collected from the signing of the ICF through the 4th week of the weekly follow-up phone call.

The parents/caregivers of patients with a current epilepsy and/or seizure diagnosis will be asked at each study visit if there has been any increase in frequency or severity of the patient's seizures. If an increase in frequency or severity is noted, this will be recorded as an AE in the CRF.

The Investigator is responsible for reviewing laboratory test results and determining whether an abnormal value represents for the patient a change from the time of signing of the ICF. In general, abnormal laboratory findings without clinical significance (based on the Investigator's judgement) should not be recorded as AEs. Clinically significant changes occurring after the signing of the ICF are considered AEs; however, the reported adverse event should include the underlying diagnosis or resulting clinical sequelae. Patients having clinically significant AEs will be followed until they return to normal or become stabilized.

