14.2. Analysis Populations

The safety analysis set will include all enrolled patients who receive at least one dose of trial drug (which includes placebo run-in).

The randomized safety analysis set will include all patients who receive at least one dose of randomized trial drug. The randomized safety analysis will be the primary population for safety analyses. The treatment group assignment for this population will be the treatment actually received.

The full analysis set (FAS) will include all patients in the randomized safety analysis set who have both a baseline and a post-baseline ABC-C_{FXS} assessment. The FAS set will serve as the primary efficacy study population. The treatment group assignment for analysis will be the treatment the patient was randomized to.

The PK population will include all patients who have at least one sample collected during treatment and analyzed for determination of the CBD and THC concentrations.

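### AE tables group events by dose at onset, with no onset window or denominator, and outside the double-blind weeks this conflicts with grouping by treatment actually received

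*Combined protocol and SAP*

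**What the plan says.** The AE rule is the same in section 14.4 and in the synopsis (Statistical Methods): "AEs will be tabulated by the actual treatment dose of trial drug received at the time of initiation of the adverse event". The only other AE table is an overall count of events and of patients with events, with no arm or period named.

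Section 14.2 makes the randomized safety set (at least one dose of randomized trial drug) the primary safety population and states: "The treatment group assignment for this population will be the treatment actually received". A wider safety set also takes in patients dosed only in the placebo run-in.

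The timing of events and doses is set elsewhere:

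- Section 12.2.1.1: "AEs will be collected from the signing of the ICF through the 4th week of the weekly follow-up phone call". Section 12.3 agrees.
- Table 3, footnote k: "At Visit 2, all patients will receive placebo for" a redacted period.
- Section 7.4: "All patients will remain on their assigned dose during the 12 weeks of the treatment phase of the study".
- Section 7.7: patients on AEDs who stop or do not enter the extension taper over one or two weeks. All patients not entering the extension are followed by telephone for four weeks after the last dose.

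The term "Treatment emergent adverse event" is in the abbreviation list, and sections 5.3.2 and 5.3.3 use it for earlier studies. Sections 12 and 14 neither define it nor apply it to this trial.

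**The concern.** The AE table is the main between-arm display of tolerability. A reader expects it to compare randomized groups over randomized treatment. The rule in 14.4 does not secure that. It sorts each event by the dose in use on the day the event began, and it is not limited to any period, although events are collected from consent to the last follow-up call.

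Taken at its word, the placebo column would mix lead-in with double-blind time and patients from both arms. The ZYN002 dose columns would hold only randomized treatment and taper. The lead-in is also each patient's first exposure to the gel vehicle, and application-site events were among the common AEs in the earlier studies described in 5.3.2, so lead-in events need not be negligible.

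**Working it through.** The plan states no figure on this point, so there is none to reproduce. The check sets the two rules side by side and then sizes the difference.

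**Where an AE goes, by period of onset**

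| Period | Section 14.4, read literally | Section 14.2 |
|---|---|---|
| Consent to Visit 2 | No dose, so no column | Patient's own group |
| Placebo lead-in | Placebo, for everyone | Patient's own group |
| 12 double-blind weeks | Placebo, 250 or 500 mg/day | Same, apart from dosing suspended under 7.6.16 |
| Taper | ZYN002 patients move to a lower-dose column, including 125 mg/day, which nobody is assigned in the double-blind weeks | Patient's own group |
| Off-drug follow-up | No column; overall count only | Patient's own group |

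An onset window is needed under either rule. Without one, 14.2 would credit ZYN002 with events that began on lead-in placebo.

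**Lead-in share of the placebo column**

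Inputs: 102 per arm (section 7.1); 12 double-blind weeks; no dropout (assumed); lead-in of L weeks. The length is redacted. L = 2 is assumed because section 7.6.1 places Visit 2 at Week −2. The range runs from 1 week to 17/7 = 2.4 weeks (2 weeks plus the 3-day visit window).

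- Placebo-column patient-weeks = 102 × (12 + L) + 102 × L = 102 × (12 + 2L)
- Share from later ZYN002 patients = L / (12 + 2L)

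| L (weeks) | Placebo-column patient-weeks | Of which from later ZYN002 patients |
|---|---|---|
| 1 | 1,428 | 102 (7.1%) |
| 2 | 1,632 | 204 (12.5%) |
| 2.4 | 1,719 | 248 (14.4%) |

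**Effect on the placebo percentage**

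Assume a constant AE rate and 12-week incidence p, so that the risk over t weeks is 1 − (1 − p)^(t/12). Take p = 41.3%, the placebo figure of the earlier epilepsy trial (26 of 63, section 5.3.3), and L = 2.

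- Risk over 2 weeks: 1 − 0.587^(2/12) = 0.085. Later ZYN002 patients with a lead-in AE: 102 × 0.085 = 8.7.
- Risk over 14 weeks: 1 − 0.587^(14/12) = 0.463. Placebo-arm patients with an AE: 102 × 0.463 = 47.2.
- Total 55.9: 54.8% of 102, or 27.4% of 204.

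| 12-week incidence (double-blind onset only) | Later ZYN002 patients counted under placebo | Placebo column, denominator 102 | Placebo column, denominator 204 |
|---|---|---|---|
| 20% | 3.7 | 26.6% | 13.3% |
| 41.3% | 8.7 | 54.8% | 27.4% |
| 60% | 14.4 | 79.8% | 39.9% |

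The column reads too high on one denominator and too low on the other. The plan names neither.

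**Follow-up and taper, per arm**

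Assume 2% to 20% do not enter the extension (98% entered in the epilepsy programme, section 5.3.4) and up to 20% use AEDs (assumed).

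- Follow-up: 4-week risk 1 − 0.587^(4/12) = 0.163. Patients with an AE: 102 × 0.02 × 0.163 = 0.3 to 102 × 0.20 × 0.163 = 3.3.
- Taper, upper end: 102 × 0.20 × 0.20 = 4.08 patients taper. Over two weeks, 4.08 × 0.085 = 0.35, so at most about 0.4 patients with an AE.
- With 60% incidence the upper ends are 102 × 0.20 × 0.263 = 5.4 and 4.08 × 0.142 = 0.6.

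**The case against.** The strongest defence is that 14.2 already answers the question. It names the randomized safety set as primary and assigns it by treatment received. Section 12.1 and the synopsis (Safety Analyses) also tie the safety analysis to at least one randomized dose. On that reading, follow-up AEs have an arm and lead-in AEs do not move to placebo. This is a fair reading, and it is why the contamination cannot be stated as certain. It does not settle the matter. Those sections select patients, not events, and none says it overrides the AE-specific sentence in 14.4. Section 14.4 itself uses actual treatment group for vital signs, laboratory tests, ECGs and skin checks, but different wording for AEs.

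A second defence is that trial drug sometimes means the active arm only, as where the synopsis speaks of randomizing to trial drug or placebo. The usage is indeed inconsistent. However, the synopsis (Duration of Treatment) has caregivers applying trial drug during the lead-in, and Table 3 marks trial drug application at Visit 2.

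Third, section 14 defers definitions to a later SAP, whose text is not in the document reviewed. That SAP could supply a window and a denominator. It would then have to depart from the rule that 14.4 states, so the protocol wording should be aligned.

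It also stands that the analysis is descriptive, that withdrawal symptoms are assessed separately by MWC and PWC-20, and that recorded onset dates allow re-tabulation.

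**Conclusion.** The point holds as an unresolved conflict between 14.4 and 14.2 outside the double-blind weeks, together with a missing onset window and denominator. It should be fixed. It does not touch efficacy.

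The material part is the lead-in: under a literal 14.4, later ZYN002 patients supply 12.5% of the placebo column's patient-weeks (7.1% to 14.4%). This rests on 102 per arm, no dropout and an assumed lead-in length. Follow-up and taper are marginal: about 0.3 to 3.3 patients with an AE per arm for follow-up and at most about 0.4 for taper, at the 41.3% incidence borrowed from another population.

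Three stronger conclusions are tempting but not supported:

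- A reader might infer that the rule biases the comparison in favour of ZYN002. The direction is unknown, because the placebo percentage can move either way with the unstated denominator.
- A reader might set 1,632 placebo patient-weeks against 102 × 12 = 1,224 for ZYN002 and expect 1.33 times as many placebo AEs. That pools ZYN002 dose columns that 14.4 keeps apart, and a ratio of event counts is not an incidence comparison.
- A reader might infer that follow-up AEs are lost. They are collected and enter the overall count; what is missing is a by-arm place for them.

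**What to change.** In section 14.4 and the synopsis:

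- Make the main AE table treatment-emergent, with onset on or after the first randomized dose, in the randomized safety set.
- Group it by treatment actually received (ZYN002 versus placebo), with dose or weight stratum as a breakdown and that set as the denominator.
- List AEs with onset before the first randomized dose separately.
- Keep taper and follow-up AEs under the patient's own treatment group.
- Retain dose at onset, if wanted, as a supplementary display.

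The cost is wording and table shells. No new data are needed, because section 12.3 already records onset dates.

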During the single-blind Placebo Lead-In period patients ≤ 35 kg will receive placebo, applied Q12H (± 2 hours). Each application will consist of one sachet of placebo containing 2.98 g of gel (two sachets in total per day). Patients > 35 kg will receive placebo, applied Q12H (± 2 hours). Each application will consist of two sachets of placebo containing 2.98 g of gel in each sachet (four sachets in total per day).

Treatment Period:

At Visit 3 patients will be randomized to either:

Treatment A (Trial Drug)

Patients ≤ 35 kg will receive 125 mg CBD applied Q12H (± 2 hours); total daily dose of 250 mg CBD. Each application will consist of one sachet of ZYN002 CBD 4.2% concentration, containing 2.98 g of gel. This dosing will continue for the duration of the study.

Patients > 35 kg will receive 250 mg CBD applied Q12H (± 2 hours); total daily dose of 500 mg CBD. Each application will consist of two sachets of ZYN002 CBD 4.2% concentration, each sachet containing 2.98 g of gel. This dosing will continue for the duration of the study.

OR

Treatment B (Placebo)

Patients ≤ 35 kg will receive placebo, applied Q12H (± 2 hours). Each application Q12H (± 2 hours), will consist of one sachet of placebo, containing 2.98 g of gel. This dosing will continue for the duration of the study.

Patients > 35 kg will receive placebo, applied Q12H (± 2 hours). Each application Q12H (± 2 hours) will consist of two sachets of placebo, each sachet containing 2.98 g of gel. This dosing will continue for the duration of the study.

Duration of Treatment:

Parents/caregivers will apply trial drug twice daily for the [REDACTED] single-blind placebo lead-in period, followed by 12 weeks of randomized treatment twice daily. Following Week 12, patients on AEDs may have an additional one or two weeks of blinded treatment to taper off trial drug.

Criteria for Evaluation:**Efficacy:**

Efficacy assessments are as indicated in [Table 3](#) Schedule of Assessments.

The primary endpoint is the change from Baseline to Week 12 in the ABC-C_{FXS} Social Avoidance subscale score.

Key Secondary Endpoints Include:

- a. Change from Baseline to Week 12 in ABC-C_{FXS} Irritability subscale score.
- b. Change from Baseline to Week 12 in ABC-C_{FXS} Socially Unresponsive/Lethargic subscale score.
- c. CGI-I at Week 12/ET.

Secondary Endpoints Include: Secondary Endpoints include:

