CBD, THC and AED Blood Samples ^l	X			X		X				
Qualitative Caregiver reported Behavioral Problems Survey	X									
Aberrant Behavior Checklist-FXS Specific (ABC-CFXS)	X	X	X	X	X	X				

	Screening	Placebo Lead-In	Double-Blind Treatment							
	Screening Visit ^a (Week -4)	Visit 2 Placebo Lead-In ^b	Visit 3 (Study Day 1) Randomization ^c	Visit 4 (Week 4)	Visit 5 (Week 8)	Visit 6 (Week 12) / Early Termination (ET)	Taper Period ^{d,e}	End of Study Visit (EOS)	Weekly Telephone Follow-Up ^e (Four Weeks)	Un- scheduled Visit(s)
	Days ¹ to Day - ²	Days ¹ to Day ²	Day 1 (± 3 days)	Day 28 (± 3 days)	Day 56 (± 3 days)	Day 84 (± 3 days)	(One-Two Weeks)	(± 3 days after Taper Period)	(± 3 days)	Skin Check Follow-up
Anxiety, Depression and Mood Scale (ADAMS)		X	X	X	X	X				
Clinical Global Impression-Severity (CGI-S)	X	X	X	X	X	X				
Clinical Global Impression-Improvement (CGI-I)			X	X	X	X				
Caregiver Global Impression of Severity		X	X			X				
Caregiver Global Impression of Change						X				
Family Impact PedsQL™		X	X			X				
Autism Diagnostic Observation Schedule® (ADOS®-2) ^m	X									
Vineland Adaptive Behavior Scales™ (VABS-3)	X									
Columbia-Suicide Severity Rating Scale (C-SSRS)	X	X	X	X	X	X	X	X	X	X
Marijuana Withdrawal Checklist -Short form (MWC)	X					X	X	X	X	
Penn Physician Withdrawal Checklist (PWC-20)	X					X	X	X	X	
Skin assessment exam ⁿ	X	X								
Skin irritation check ^o		X	X	X	X	X		X		X
Skin irritation check diary (daily) ^o		X	X	X	X	X	X	X		X
Adverse events	X	X	X	X	X	X	X	X	X	X
IQ Test Results (optional) ^p	X									

Table 3 Footnotes

- a. The Screening visit procedures can be split into multiple visits for those patients whom the Investigator determines it would be difficult for the patient to undergo all Screening assessments on one day. The first part of the Screening procedures will include eligibility criteria.
- b. If Visit 2 is split into multiple days, ABC-C_{FXS}, ADAMS, CGI-S and Family Impact PedsQL™ should be performed on the same day.
- c. Patients will receive blinded study medication for the month between scheduled visits. Medication dispensed at Visit 3 will include either four weeks of placebo OR four weeks of 125 mg Q12H OR four weeks of 250 mg Q12H.

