11.4. Method of Treatment Assignment or Randomization

Patients will be randomly assigned to treatment according to a computer generated randomization scheme. Randomization will be coordinated centrally through an interactive response system (IRT). The system will provide patient identification numbers at Screening, which are subsequently linked to the treatment assignments at randomization. Following completion of all evaluations at Visit 3, patients who meet all eligibility requirements and randomization criteria will be randomly allocated to active or placebo treatment groups using a 1:1 allocation ratio. Randomization will be stratified by gender (Male vs. Female), weight (≤ 35 kg vs. > 35 kg) and region (North America vs. non-North America).

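### AE columns by dose compare lighter with heavier children; show each dose beside placebo from its own weight stratum

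*Combined protocol and SAP*

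**What the plan says.** **AE tables.** Section 14.4 states that "AEs will be tabulated by the actual treatment dose of trial drug received at the time of initiation of the adverse event", classified by system organ class and preferred term, with overall totals in addition. The Statistical Methods part of the Synopsis repeats this.

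**How dose is set.** The Synopsis gives "Patients ≤ 35 kg will receive 125 mg CBD applied Q12H (± 2 hours); total daily dose of 250 mg CBD" and "Patients > 35 kg will receive 250 mg CBD applied Q12H (± 2 hours); total daily dose of 500 mg CBD". Section 7.4 adds that "All patients will remain on their assigned dose during the 12 weeks of the treatment phase of the study". Placebo patients use one or two sachets per application according to the same 35 kg cut (Synopsis; Section 9.1).

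**What is randomized.** Allocation is 1:1 to active or placebo. Section 11.4 says that "Randomization will be stratified by gender (Male vs. Female), weight (≤ 35 kg vs. > 35 kg) and region". The weight stratum therefore has the same cut as the dose.

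**Other safety summaries.** In Section 14.4, "Application site irritation check will be summarized using counts and percentages at each respective site check score", by actual treatment group. Vital signs, laboratory tests and ECGs are grouped in the same way. None of these is planned by dose.

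**After Week 12.** Section 7.7 and Table 3 footnote d describe a taper for patients on AEDs who do not enter the extension or who stop early. Those above 35 kg pass through 250 and then 125 mg/day.

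**The concern.** A table with a 250 mg/day column and a 500 mg/day column invites the reader to look for a dose relation. Here nobody is randomized between the doses. In the double-blind weeks the two columns hold different kinds of patient, separated at 35 kg in a population aged 3 to under 18 years, so weight, and with it age, moves with dose.

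If both columns are set against one placebo column, that column mixes the two weight bands. It also mixes two vehicle loads, because heavier placebo patients apply twice the gel. Each dose is then read against a control that differs from it in weight, age and gel amount. A real excess at one dose could be masked, or an age or vehicle difference could be taken for a dose effect. The right control for each dose is already in the trial, created by the stratified randomization, but Section 14.4 describes no AE display that uses it.

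**Working it through.** **Inputs from the documents.** Sachet: 2.98 g of 4.2% gel. Applications: every 12 hours, one sachet (≤35 kg) or two (>35 kg). Sample size: 102 per arm. The documents give no AE rate by weight or age and no expected weight split, so those are assumed below.

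**The plan's own figures.**
- Dose: 2.98 g × 4.2% = 125.16 mg per sachet. Two sachets a day give 250.3 mg and four give 500.6 mg, which agrees with the stated daily doses.
- Sample size: for a 1.3-point difference and SD 2.8, a two-sided 5% t-test needs 99 per arm for 90% power. At 102 per arm the power is 91%, close to the stated 90%. The point does not depend on this; 102 is used only to give 51 per band under an even split.

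**Vehicle load on placebo.** 2 × 2.98 = 5.96 g/day at ≤35 kg; 4 × 2.98 = 11.92 g/day at >35 kg.

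**Distortion from one placebo column.** Let s be the share of patients ≤35 kg, bL and bH the placebo AE risks in the lighter and heavier bands, and dL and dH the true drug effects.
- Pooled placebo = s·bL + (1 − s)·bH
- Apparent 250 mg/day difference = bL + dL − pooled = dL + (1 − s)(bL − bH)
- Apparent 500 mg/day difference = bH + dH − pooled = dH − s(bL − bH)

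The contrast between the two columns is therefore off by bL − bH, whatever the split. Against placebo from the same band, the differences are dL and dH exactly.

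| s | bL / bH | True effect, 250 / 500 | Pooled placebo | Apparent, 250 / 500 |
|---|---|---|---|---|
| 50% | 60% / 40% | 0 / 0 | 50% | +10 / −10 |
| 40% | 60% / 40% | 0 / 0 | 48% | +12 / −8 |
| 60% | 60% / 40% | 0 / 0 | 52% | +8 / −12 |
| 50% | 50% / 40% | 0 / 0 | 45% | +5 / −5 |
| 50% | 40% / 60% | 0 / 0 | 50% | −10 / +10 |
| 50% | 50% / 50% | 0 / 0 | 50% | 0 / 0 |
| 50% | 60% / 40% | +5 / +15 | 50% | +15 / +5 |
| 50% | 50% / 40% | +5 / +15 | 45% | +10 / +10 |

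(Effects in percentage points.) The first five rows create a dose relation where there is none, the seventh reverses a real one and the last hides one. With equal background risk there is no distortion.

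**How visible it would be.** Take 60% against 40% with 51 patients in each dose column and no drug effect. The standard error is √(2 × 0.25/51) = 0.0990 under the null and √(0.48/51) = 0.0970 under these rates. The chance of a nominal p < 0.05 between the columns is Φ((0.20 − 1.96 × 0.0990)/0.0970) = Φ(0.06), about 52%. At 50% against 40% it is about 17%. The plan contains no such test; this only gauges how striking the columns could look.

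**Taper.** An AE that starts while a heavier patient is tapering is counted at 250 or 125 mg/day. It then joins a column otherwise made up of lighter patients, or a 125 mg/day column. Section 14.4 does not define denominators for these.

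**The case against.** **A single placebo column is not stated.** This is correct. Table 3 footnote c lists "either four weeks of placebo OR four weeks of 125 mg Q12H OR four weeks of 250 mg Q12H", but it describes what is dispensed at Visit 3 and does not name table columns. The protocol sometimes uses trial drug to include placebo (Section 14.2 counts the placebo run-in as trial drug), so a table by dose could conceivably split placebo by gel amount. One column remains the natural reading, since placebo has no mg dose and the arms are labelled Treatment A and Treatment B. It is still an inference.

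**Skin irritation scores.** A reader might infer that these would also show a false dose relation. The documents do not support that. The scores are planned by actual treatment group. Read as active versus placebo, randomization stratified at 35 kg balances weight, and gel load follows the same cut. The same holds for laboratory tests, ECGs and vital signs. The concern reaches skin findings only when they are recorded as AEs, as Section 7.6.16 requires for a score of 4.

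**Layout may be settled later.** Section 14 defers detail to a SAP written after protocol approval, and the text reviewed has no table shells. One can say only that Section 14.4 does not describe a weight-matched display, not that none will exist.

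**The size rests on assumed rates, and the tables are descriptive.** Both are true. No dose-response test is planned, so interpretation is at stake, not the type I error rate.

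**Conclusion.** The point holds in a limited form and is a cheap improvement. During the 12 double-blind weeks the AE dose columns are a non-randomized contrast of patients ≤35 kg with patients >35 kg. Section 14.4 describes no comparison of each dose with the weight-matched and volume-matched placebo stratum that the trial already creates.

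The bias against placebo depends on two things the documents leave open: whether placebo is shown as one column, and whether background AE risk differs between the weight bands. Its size and direction are unknown. Under the assumed 60% and 40% background risks and an even split it is +10 and −10 points; under equal risks it is zero.

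Two further readings should be avoided. Dose is not tied to weight throughout the study, because the taper breaks the link. Nor is the overall ZYN002-versus-placebo safety comparison undermined: if AEs are tabulated by arm, it is protected by the stratified randomization.

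**What to change.** In Section 14.4 and the Synopsis:

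1. Show AEs starting in the double-blind period in matched pairs by randomization weight stratum: ZYN002 250 mg/day beside placebo ≤35 kg, and ZYN002 500 mg/day beside placebo >35 kg.
2. Keep overall ZYN002 and overall placebo columns.
3. List AEs that start in the taper period separately, so that they do not enter the double-blind dose columns.
4. State that the two dose columns are not a dose-response comparison, and that each is to be read only against its own placebo column.

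A display of application-site scores by weight stratum is an optional supplement.

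The cost is SAP and table-shell wording; the data and the stratum are already collected. The drawback is smaller cells, about 51 patients per column if the weight bands are equal, which is thin for uncommon events. Keeping the overall columns offsets this.
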